7 SAFETY REPORTING REQUIREMENTS/DATA AND SAFETY MONITORING PLAN

7.1 DEFINITIONS

7.1.1 Adverse Event

Any untoward medical occurrence in a human subject, including any abnormal sign (for example, abnormal physical exam or laboratory finding), symptom, or disease, temporally associated with the subject's participation in research, whether or not considered related to the subject's participation in the research.

7.1.2 Suspected adverse reaction

Suspected adverse reaction means any adverse event for which there is a reasonable possibility that the drug caused the adverse event. For the purposes of IND safety reporting, 'reasonable possibility' means there is evidence to suggest a causal relationship between the drug and the adverse event. A suspected adverse reaction implies a lesser degree of certainty about causality than adverse reaction, which means any adverse event caused by a drug.

7.1.3 Unexpected adverse reaction

An adverse event or suspected adverse reaction is considered "unexpected" if it is not listed in the investigator brochure or is not listed at the specificity or severity that has been observed; or, if an investigator brochure is not required or available, is not consistent with the risk information described in the general investigational plan or elsewhere in the current application. "Unexpected", also refers to adverse events or suspected adverse reactions that are mentioned in the investigator brochure as occurring with a class of drugs or as anticipated from the pharmacological properties of the drug, but are not specifically mentioned as occurring with the particular drug under investigation.

7.1.4 Serious

An Unanticipated Problem or Protocol Deviation is serious if it meets the definition of a Serious Adverse Event or if it compromises the safety, welfare or rights of subjects or others.

7.1.5 Serious Adverse Event

An adverse event or suspected adverse reaction is considered serious if in the view of the investigator or the sponsor, it results in any of the following:

- Death,
- A life-threatening adverse drug experience
- Inpatient hospitalization or prolongation of existing hospitalization
- Persistent or significant incapacity or substantial disruption of the ability to conduct normal life functions
- A congenital anomaly/birth defect.
- Important medical events that may not result in death, be life-threatening, or require hospitalization may be considered a serious adverse drug experience when, based upon appropriate medical judgment, they may jeopardize the patient or subject and may require medical or surgical intervention to prevent one of the outcomes listed in this definition.

7.1.6 Disability

A substantial disruption of a person's ability to conduct normal life functions.

7.1.7 Life-threatening adverse drug experience

Any adverse event or suspected adverse reaction that places the patient or subject, in the view of the investigator or sponsor, at immediate risk of death from the reaction as it occurred, i.e., it does not include a reaction that had it occurred in a more severe form, might have caused death.

7.1.8 Protocol Deviation (NIH Definition)

Any change, divergence, or departure from the IRB-approved research protocol.

7.1.9 Non-compliance (NIH Definition)

7.1.10 The failure to comply with applicable NIH Human Research Protections Program (HRPP) policies, IRB requirements, or regulatory requirements for the protection of human research subjects. Unanticipated Problem

Any incident, experience, or outcome that:

- Is unexpected in terms of nature, severity, or frequency in relation to
 - (a) the research risks that are described in the IRB-approved research protocol and informed consent document; Investigator's Brochure or other study documents, and
 - (b) the characteristics of the subject population being studied; **AND**
- Is related or possibly related to participation in the research; **AND**
- Suggests that the research places subjects or others at a *greater risk of harm* (including physical, psychological, economic, or social harm) than was previously known or recognized.

7.2 RELATIONSHIP TO THERAPY

The Principal Investigator will assess whether the AE or SAE is associated with the administration of quadrivalent HPV (Types 6, 11, 16, 18) recombinant vaccine:

- “Related” includes, possible, probably, and definitely related events.
- “Not related” includes unlikely and not related.

7.3 NIH INTRAMURAL IRB AND CLINICAL DIRECTOR (CD) REPORTING

7.3.1 NIH Intramural IRB and NCI CD Expedited Reporting of Unanticipated Problems and Deaths

The Protocol PI will report in the NIH Problem Form to the NIH Intramural IRB and NCI CD:

- All deaths, except deaths due to progressive disease
- All Protocol Deviations
- All Unanticipated Problems
- All non-compliance

Reports must be received by within 7 days of PI awareness via iRIS.

7.3.2 NIH Intramural IRB Requirements for PI Reporting at Continuing Review

The protocol PI will report to the NIH Intramural IRB:

1. A summary of all protocol deviations in a tabular format to include the date the deviation occurred, a brief description of the deviation and any corrective action.
2. A summary of any instances of non-compliance
3. A tabular summary of the following adverse events:
 - All Grade 2 **unexpected** events that are possibly, probably or definitely related to the research;
 - All Grade 3 and 4 events that are possibly, probably or definitely related to the research;
 - All Grade 5 events regardless of attribution;
 - All Serious Events regardless of attribution.

NOTE: Grade 1 events are not required to be reported.

7.3.3 NCI-IRB Reporting of IND Safety Reports

Only IND Safety Reports that meet the definition of an unanticipated problem will need to be reported to the NCI IRB.

7.4 FDA REPORTING CRITERIA

7.4.1 IND Safety Reports to the FDA (Refer to 21 CFR 312.32)

7.4.1.1 Expedited reporting to the FDA

The Sponsor will notify FDA via phone, fax, or email of any unexpected fatal or life-threatening suspected adverse reactions as soon as possible but no later than 7 calendar days of initial receipt of the information. This will be followed with a written report within 15 days using the MedWatch Form 3500a.

The study Sponsor will notify FDA in writing of any suspected adverse reaction that is both serious and unexpected as soon as possible but no later than 15 calendar days after initial receipt of the information using the MedWatch Form 3500a. If FDA requests any additional data or information, the sponsor must submit it to the FDA as soon as possible, but no later than 15 calendar days after receiving the request.

- The study Sponsor will also report expeditiously as above:
any findings from clinical, epidemiological, or pooled analysis of multiple studies or any findings from animal or in vitro testing that suggest a significant risk in humans exposed to the drug
- clinically important increase in the rate of a serious suspected adverse reaction over that listed in the protocol or investigator brochure.

7.4.2 FDA Annual Reports (Refer to [21 CFR 312.33](#))

The study Sponsor will submit a brief report annually of the progress of the trial within 60 days of the anniversary date that the IND went into effect as indicated in 21CFR 312.33, and any associated FDA correspondences regarding the IND annual report. The Annual Report will include:

- A summary of the status of the trial, including the title of the study, protocol number, purpose (objectives), a description of the patient population, and a statement as to whether the study has been completed or is ongoing.

- The accrual ceiling and the number enrolled, tabulated by age group, gender, and race. The number whose participation in the study was completed as planned and the number who withdrew from the study for any reason.
- Once the study is completed, a brief description of the results should be reported.
- A narrative or tabular summary of the most frequent and most serious adverse experiences by body system.
- A summary of all IND Safety Reports
- A list of subjects who died during participation with the cause of death for each subject.
- A list of subjects who withdrew prematurely during the course of the study in association with any adverse experience, whether or not it was thought to be associated to GARDASIL®
- A description of any protocol modifications during the past year if not previously reported.
- A description of the general investigation plan for the coming year.

7.4.4 Adverse Vaccine Reactions

Adverse vaccine reactions will be reported to the FDA, the IRB and Merck, as well as to the U.S. Department of Health and Human Services Vaccine Adverse Event Reporting System (VAERS): [name] or on line at www.vaers.hhs.gov. These will be reported within 10 working days. If the event is a SAE or a previously unknown toxicity, it will be reported to the IRB, Merck and the FDA as outlined above. All first occurrences of adverse reactions judged to be related to quadrivalent HPV vaccine will be considered unexpected reactions for the purpose of reporting.

7.5 DATA AND SAFETY MONITORING PLAN

7.5.1 Principal Investigator/Research Team

This phase I, prospective study will be monitored by the Principal Investigator and as required by the FDA as part of the Sponsor Investigator IND held by the Principal Investigator. Based on the minimal level of risk and the number of subjects to be studied, monitoring by a single independent monitor or a data and safety monitoring board (DSMB) is not warranted. Specifically, the protocol is investigating the use of a FDA approved, licensed vaccine in a unique population and vaccine immunogenicity rather than safety is likely to be the most critical outcome finding of this study, particularly given the provisional recommendations of the ACIP for the Use of Quadrivalent HPV Vaccine.⁸⁴

Clinical, laboratory and adverse event data will be monitored a minimum of once monthly or more frequently as accrual to the study increases. From an adverse event, risk and safety-reporting standpoint, the study will be monitored for:

- Excess adverse or vaccine-related events observed in study subjects compared to events reported in clinical trials involving vaccine and placebo subjects.
- *Novel* adverse or vaccine-related events not previously reported in clinical licensing trials of the vaccine.
- Evidence of increased viral replication as measured by serial HIV-1 RNA levels (Days 1,3 and 7) following the first quadrivalent HPV vaccination in HIV-infected individuals.

Clinical research team and medical staff will notify the Principal Investigator of any suspected SAEs with subsequent reporting as previously outlined in 5.3.1.3. The study research nurse coordinator and/or data manager will generate a bi-weekly (or weekly) report of all on-study laboratory data with correspondent toxicity grading according to CTCAE v3.0 as well as a summary of all clinical and Vaccine Report Card (VRC) surveillance adverse event data for review by The Principal Investigator, the Lead Associate Investigator or their designee.

7.5.2 Sponsor Monitoring Plan

NOTE: As the IND is withdrawn/no longer active, Sponsor monitoring activities are no longer ongoing. This trial will be monitored by personnel employed by a CCR contractor to the NCI, NIH. Monitors are qualified by training and experience to monitor the progress of clinical trials. Personnel monitoring this study will not be affiliated in any way with the trial conduct.

At least 25% of enrolled patients' will be randomly selected and monitored at least quarterly, based on accrual rate. The patients selected will have 100% source document verification done. Additional monitoring activities will include: adherence to protocol specified study eligibility, treatment plans, data collection for safety and efficacy, reporting and time frames of adverse events to the IRB and FDA, and informed consent requirements. Written reports will be generated in response to the monitoring activities and submitted to the Principal investigator and Clinical Director or Deputy Clinical Director, CCR, NCI.

8 HUMAN SUBJECTS PROTECTIONS

8.1 RATIONALE FOR SUBJECT SELECTION

8.1.1 General

As outlined in section 1.2.6 this study seeks to enroll subjects at risk for acquisition of HPV infection (pre-adolescents, adolescents and young adults 12-26 years of age) and at risk for excess HPV-related morbidity once infected i.e. HIV-infected males and females. Vaccine immunogenicity will be studied in HIV-infected individuals with identical CD4 and viral load parameters at entry who are on HAART (Cohort 1) and not receiving HAART (Cohort 2). The latter cohort will allow assessment of quadrivalent HPV recombinant vaccine immunogenicity and safety in a population similar to those found in developing countries with little or no access to antiretroviral treatment where there is also a concomitant, high burden of prevalent HPV and HIV disease. Both HIV-infected cohorts will permit assessment of whether HPV vaccination is associated with alterations in HIV-1 RNA levels and the impact of CD4 count and viral load on vaccine immunogenicity. In addition, comparison between cohorts will allow assessment of the impact of HAART on vaccine immunogenicity.

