1 INTRODUCTION

1.1 STUDY OBJECTIVES

The **primary** objectives of this study are to:

- Assess the immunogenicity and safety of the quadrivalent human papillomavirus (types 6, 11, 16, 18) 3

The **secondary** objectives of this study are to:

- Determine whether there are differences in HPV vaccine immunogenicity between HIV-infected and HIV uninfected age-matched controls.
- Determine whether there are differences in HPV vaccine immunogenicity between HIV-infected patients receiving highly active antiretroviral therapy (HAART) and those not receiving HAART with similar CD4 and viral load parameters at entry.
- Determine whether HPV vaccination alters HIV-1 RNA levels.
- Investigate the impact of CD4 count and HIV-1 RNA levels on HPV vaccine immunogenicity.
- Characterize HPV DNA positivity by oral/buccal and anogenital swabs at baseline in the study cohort populations.
- Characterize HPV and HIV knowledge and risk and sexual behaviors in the study cohort populations.

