1.2.6 Rationale for Study Cohort Population

This study will be conducted in both HIV-infected females and males 12-26 years of age. Since the risk of HPV acquisition is intensified during adolescence and young adulthood because of risk-taking and exploratory behaviors and because of the well-documented co-morbidities associated with sexually acquired HPV in individuals with HIV infection, both males and females are included in the study. It is anticipated that Cohort 1 will be comprised primarily (but not exclusively) of sexually naïve pre-adolescents and adolescents infected with HIV vertically or by transfusion early in life that have experienced successful immune reconstitution and viral load reduction on HAART therapy (i.e. CD4 count ≥ 350 cells/mm³ and HIV-1 RNA levels $\leq 20,000$ copies/ml). This population represents an ideal one to investigate vaccine immunogenicity given the high likelihood of HPV acquisition following the initiation of sexually activity.

It is anticipated that Cohort 2 will be comprised primarily (but not exclusively) of adolescents and young adults with sexually acquired HIV infection that have no current indication for HAART therapy according to current USPHS Treatment Guidelines (i.e. CD4 count ≥ 500 cells/mm³ and HIV-1 RNA levels $\leq 20,000$ copies/ml).⁹⁸ These individuals represent a unique population to assess HPV vaccine immunogenicity and safety that parallels populations in developing countries with little or no access to antiretroviral treatment where there is a high burden of prevalent HPV and HIV disease. Both Cohorts 1 and 2 will permit assessment of whether HPV vaccination is associated with alterations in HIV-1 RNA levels and if observed, whether alterations are mitigated in the presence of HAART. In addition, both HIV-infected cohorts will allow investigation of the impact of CD4 count and HIV-1 RNA levels on HPV vaccine immunogenicity.

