2 ELIGIBILITY ASSESSMENT AND ENROLLMENT

2.1 ELIGIBILITY CRITERIA

2.1.1 Cohort 1 Inclusion and Exclusion Eligibility Criteria

Inclusion Criteria

- 2.1.1.1 Age 12 to 26 years
- 2.1.1.2 Females and males
- 2.1.1.3 HIV-positive
- 2.1.1.4 CD4 cell count and HIV-1 RNA level parameters
 - 2.1.1.4.1 CD4 cell count \geq 350 cells/mm³
 - 2.1.1.4.2 HIV-1 RNA level by RT PCR \leq 20,000 copies/ml
- 2.1.1.5 On stable HAART regimen for > 6 months with CD4 and viral load parameters as outlined in 2.1.1.4
- 2.1.1.6 Patients > 18 years willing to provide informed consent or parent/guardian willing to provide informed consent for minor children <18 years of age.
- 2.1.1.7 Informed assent for patients 12-17 years of age (Optional at the discretion of the Principal Investigator and Parent/Guardian based on maturity level of minor)
- 2.1.1.8 Willing to use acceptable forms of contraception, if applicable, or abstinence to prevent pregnancy.

Exclusion Criteria

- 2.1.1.9 Any of the following hematologic abnormalities
 - 2.1.1.9.1 Hemoglobin < 10.0 g/dL
 - 2.1.1.9.2 Neutrophil count < 1500/mm³
 - 2.1.1.9.3 Platelet count < 75,000/mm³
 - 2.1.1.9.4 PT or PTT \geq 1.5X ULN (with the exception of patients with known clotting disorders or known lupus anticoagulant).
- 2.1.1.10 Any of the following hepatic abnormalities

- 2.1.1.10.1 ALT/SGPT and/or AST/SGOT > 2.5X ULN
- 2.1.1.10.2 Total bilirubin > 1.5X ULN unless attributable to protease inhibitor therapy.
- 2.1.1.11 Positive tests (antibody and/or antigen) for hepatitis B and hepatitis C viruses, unless the result is consistent with prior vaccination or prior infection with full recovery.
- 2.1.1.12 Acute infection requiring therapy at time of enrollment. Participants may be eligible for study after being on stable and appropriate anti-infective therapy.
- 2.1.1.13 Chemotherapy for active cancer.
- 2.1.1.14 Documented history of non-adherence to antiretroviral treatment regimen within 12 months of study entry.
- 2.1.1.15 Pregnancy or breastfeeding.
- 2.1.1.16 Use of immunosuppressive or immunomodulating agents within 8 weeks of study enrollment. Note: patients receiving oral corticosteroids for management of asthma or contact hypersensitivity for < 14 days in duration will be allowed to enroll as long as it has been > 30 days since oral corticosteroid administration.
- 2.1.1.17 Known immediate hypersensitivity to yeast or any of the vaccine components.

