2.1.2 Cohort 2 Inclusion and Exclusion Eligibility Criteria

Inclusion Criteria

- 2.1.2.1 Age 12 to 26 years
- 2.1.2.2 Females and males
- 2.1.2.3 HIV-positive
- 2.1.2.4 CD4 cell count and HIV-1 RNA level parameters
 - 2.1.2.4.1 CD4 cell count \geq 500 cells/mm³
 - 2.1.2.4.2 HIV-1 RNA level by RT PCR \leq 20,000 copies/ml.
- 2.1.2.5 *Not* receiving antiretroviral treatment with CD4 and viral load parameters as outlined in 2.1.2.4.
- 2.1.2.6 Patients \geq 18 years willing to provide informed consent or parent/guardian willing to provide informed consent for minor children <18 years of age.
- 2.1.2.7 Informed assent for patients 12-17 years of age (Optional at the discretion of the Principal Investigator and Parent/Guardian based on maturity level of minor)
- 2.1.2.8 Willing to use acceptable forms of contraception, if applicable, or abstinence to prevent pregnancy.

Exclusion Criteria

- 2.1.2.9 Any of the following hematologic abnormalities:
 - 2.1.2.9.1 Hemoglobin < 10.0 g/dL
 - 2.1.2.9.2 Neutrophil count < 1500/mm³
 - 2.1.2.9.3 Platelet count < 75,000/mm³
 - 2.1.2.9.4 PT or PTT \geq 1.5X ULN (with the exception of patients with known clotting disorders or known lupus anticoagulant).
- 2.1.2.10 Any of the following hepatic abnormalities
 - 2.1.2.10.1 ALT/SGPT and/or AST/SGOT > 2.5X ULN
 - 2.1.2.10.2 Total bilirubin > 1.5X ULN unless attributable to protease inhibitor therapy.
- 2.1.2.11 Positive tests (antibody and/or antigen) for hepatitis B and hepatitis C viruses, unless the result is consistent with prior vaccination or prior infection with full recovery.
- 2.1.2.12 Acute infection requiring therapy at time of enrollment. Participants may be eligible for study after being on stable and appropriate anti-infective therapy.
- 2.1.2.13 Chemotherapy for active cancer.
- 2.1.2.14 Pregnancy or breastfeeding.
- 2.1.2.15 Use of immunosuppressive or immunomodulating agents within 8 weeks prior to study enrollment. Note: patients receiving oral corticosteroids for management of asthma or contact hypersensitivity for \leq 14 days in duration will be allowed to enroll as long as it has been \geq 30 days since oral corticosteroid administration.
- 2.1.2.16 Known immediate hypersensitivity to yeast or any of the vaccine components.
- 2.1.2.17 Use of investigational agents within 4 weeks prior to study enrollment.
- 2.1.2.18 Active external genital warts requiring treatment or CIN 2/3.

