HIV positive and healthy, HIV negative subjects 12 to 26 years of age are needed as volunteer human research subjects for a study to evaluate the immunogenicity of the quadrivalent human papilloma virus (types 6, 11, 16, 18) recombinant vaccine. This vaccine was approved and licensed by the FDA for clinical use on June 8, 2006 and is marketed under the name GARDASIL®. In healthy, HIV-negative, women, vaccination with GARDASIL® induces immune responses i.e. neutralizing antibody titers to the four HPV virus types that are in the vaccine: types 6, 11, 16, and 18. These HPV types are associated with the development of genital warts and precancerous lesions of the cervix and cervical cancer. The vaccine was demonstrated to be highly (100%) effective in preventing the conditions listed above in individuals with normal immune systems. However, it is not known whether the vaccine will be as effective in generating antibody responses or if the responses will last as long, in individuals whose immune systems are compromised, such as individuals with HIV-infection. Since individuals with HIV-infection are at greater risk of becoming infected with HPV and developing pre-cancerous complications from it, both females and males are being included in this study. HIV negative subjects are being studied at the same time as HIV positive subjects in order to directly compare how well the vaccine is able to induce antibodies compared to a healthy age-matched population. The study is four years long and involves 7 study visits the first year and then 1 study visit every six months (2 visits per year) during years 2 through 4.

[figure not shown]
Persons with HIV-infection must have greater than 350 CD4 cells/mm³ and a viral load \leq 20,000 copies/ml. They may be on HAART therapy or no antiretroviral treatment. Healthy, normal volunteers will have to agree to undergo HIV testing to participate in the study. Study-related screening and diagnostic tests will be performed at the NIH Clinical Research Center in Bethesda, MD without charge. Quadrivalent HPV (types 6, 11, 16, 18) recombinant vaccine will be provided free to all study subjects. For volunteers who live $>$ 50 miles from the NIH, transportation costs will be provided after the first visit if the individual is found to be eligible and enrolls in the study.

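### Section 8.1.1 describes the two HIV cohorts as matched on CD4 at entry and reads their comparison as the impact of HAART; the eligibility criteria and the analysis plan support only a difference between cohorts

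*Combined protocol and SAP*

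**What the plan says.** **Entry criteria.** Section 8.1.1 describes the HIV cohorts as "HIV-infected individuals with identical CD4 and viral load parameters at entry who are on HAART (Cohort 1) and not receiving HAART (Cohort 2". The criteria differ on CD4: "CD4 cell count \geq 350 cells/mm³" in 2.1.1 for Cohort 1 and "CD4 cell count \geq 500 cells/mm³" in 2.1.2 for Cohort 2. The Precis and 1.2.6 repeat the two floors. The HIV-1 RNA ceiling of 20,000 copies/ml is the same in both. Appendix 11, the recruitment summary, gives a single CD4 figure: "Persons with HIV-infection must have greater than 350 CD4 cells/mm³ and a viral load" at or below the ceiling, and "They may be on HAART therapy or no antiretroviral treatment".

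**Question.** Section 1.1 lists as a secondary objective the comparison of patients on HAART with "those not receiving HAART with similar CD4 and viral load parameters at entry". Section 8.1.1 goes further: "comparison between cohorts will allow assessment of the impact of HAART on vaccine immunogenicity". Section 5.2 places use of HAART among secondary analyses said to be set out in the statistical section. Section 6.1 nevertheless makes Cohort 1 vs 2 one of four primary comparisons at 0.0125, and 6.2 repeats it at four timepoints at 0.003.

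**Population.** The study is not randomised (3.1). Section 1.2.6 expects Cohort 1 to be mainly "pre-adolescents and adolescents infected with HIV vertically or by transfusion early in life", and Cohort 2 to be mainly adolescents and young adults infected sexually.

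**Analysis.** Sections 6.1 and 6.2 name no covariate, matching or restriction for Cohort 1 vs 2. The mixed model in 6.2 is optional and names no covariates. Section 6.4 is an exploratory correlation of fold increase in titer with baseline CD4 and viral load.

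**The concern.** The objective asks about HAART at similar CD4, and 8.1.1 treats that similarity as built into eligibility. It is not: Cohort 1 may include patients with CD4 of 350 to 499, and Cohort 2 can have none at entry. The protocol also expects the cohorts to differ in age and in route and duration of infection, and no planned analysis makes them comparable or checks whether they are. A difference in titer due to CD4 or age could be reported as an effect of HAART, or could mask one. What is at stake is the meaning of the Cohort 1 vs 2 result, not the validity of the test.

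**Working it through.** **1. What the stated power implies about the test.** Inputs from 6.1: 35 per cohort, effect 1.0 SD, alpha 0.0125 (two-sided assumed, since 6.1 does not say). For a plain two-sample t-test the noncentrality is 1/√(1/35 + 1/35) = 4.18 on 68 df, and power is 94.4% (stated: at least 94%). At the 0.003 of 6.2 the same test gives 86.0% (stated 85%), and 70 vs 35 gives 96.1% (stated 96%). The plan's figures therefore reproduce and match a comparison without covariates. Section 6.1 does not name the test, so *unadjusted* is inferred from this match and from the absence of any covariate.

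**2. Is similarity secured elsewhere?** Age and gender comparability is described only for the HIV-negative controls (1.2.6, 3.1). Section 5.2 promises a secondary analysis of use of HAART (citing a section 5.4 that does not exist; section 6 is evidently meant). Section 6.4 covers CD4 and viral load only, so section 6 contains no secondary analysis of HAART use.

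**3. How much could the CD4 floors alone matter?** The documents give no CD4 distribution and no CD4-titer correlation, so this is an illustration. Assume one underlying normal CD4 distribution with mean μ = 500 to 800 and SD 250, truncated at 350 (Cohort 1) and 500 (Cohort 2), a correlation r between CD4 and log titer of 0.1 to 0.5, and no HAART effect.

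- The mean above a floor c is μ + 250·φ(z)/(1 − Φ(z)), with z = (c − μ)/250.
- For μ = 500 the cohort means are 615 and 700 and the SDs 179 and 151. The standardised gap is D = 84.7/165.6 = 0.51.
- For μ = 800 the means are 820.5 and 854.9, and D = 34.4/218.9 = 0.16.
- The titer difference due to CD4 is r × D, from 0.1 × 0.157 = 0.02 SD to 0.5 × 0.512 = 0.26 SD.

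Probability of a significant result (%) at alpha 0.0125, 35 vs 35, from the noncentral t with effect r × D (nominal 1.25):

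| μ | D | r = 0.1 | r = 0.2 | r = 0.3 | r = 0.5 |
|---|---|---|---|---|---|
| 500 | 0.51 | 1.44 | 2.06 | 3.16 | 7.34 |
| 600 | 0.37 | 1.35 | 1.67 | 2.22 | 4.17 |
| 700 | 0.25 | 1.30 | 1.44 | 1.68 | 2.50 |
| 800 | 0.16 | 1.27 | 1.32 | 1.41 | 1.72 |

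Fourteen of the 16 cells are at or below 3.2%. At alpha 0.003 the range is 0.31% to 2.7%. In the other direction, a shift of 0.25 SD against a true 1 SD effect leaves 0.75 SD and reduces power at 0.0125 from 94% to 71%. Age is not in this illustration; its contribution is additional and not quantified.

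**4. Precision of supportive analyses.** Adding age and CD4 multiplies the variance of the cohort difference by (1 + ΣD²/4)(1 − R²), where R² is the share of within-cohort titer variance explained.

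- Two gaps of 0.5 SD: 1.125 at R² = 0 (standard error up 6%), 0.84 at R² = 0.25 (down 8%).
- Two gaps of 1 SD: 1.5 at R² = 0 (up 22%), 1.125 at R² = 0.25 (up 6%).
- Restricting Cohort 1 to CD4 of at least 500 keeps 69% to 92% of it, 24 to 32 of 35. With 24 the standard error rises by √[(1/24 + 1/35)/(2/35)] = 1.11, or 11%; with 32, by 2%.

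**The case against.** The strongest reply is that this is mainly one inaccurate word. Section 8.1.1 refers back to 1.2.6, which gives the correct floors. Section 1.1 says similar rather than identical, and its parameters can be read as the entry criteria, not measured values. Enrolment runs on 2.1.1 and 2.1.2, which are clear. Appendix 11 states a minimum that every Cohort 2 patient also meets, and an untreated volunteer at 350 to 499 would be screened out. All of this limits the consequences. It does not rescue the claim in 8.1.1, because floors of 350 and 500 are not identical and no analysis supports the causal reading.

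A reader might infer that the Cohort 1 vs 2 test should itself be replaced by a CD4-adjusted model. The documents do not support that. Section 1.2.6 describes both immune reconstitution and viral load reduction on HAART, so CD4 in Cohort 1 is partly a result of treatment, and conditioning on it is a choice of estimand. Adjustment also relies on extrapolation at 350 to 499, where Cohort 2 has nobody at entry. With two covariate gaps of 1 SD, power at 0.003 would be 63% (R² = 0) to 80% (R² = 0.25), against the stated 85%. The objection to moving the alpha therefore stands.

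**Conclusion.** The concern holds as a limit on interpretation. The wording of 8.1.1 contradicts the eligibility criteria, and the planned comparison answers whether titers differ between cohorts, not what HAART does at similar CD4. The secondary analysis of HAART use promised in 5.2 is missing, and the question is secondary in 1.1 and 5.2 but primary in 6.1.

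Two stronger conclusions might be drawn, and neither is supported. One is that the 6.1 test is invalid or its type I error inflated: for the question 6.1 asks, it is not. The other is that the comparison is known to be materially biased: floors do not fix the CD4 distributions achieved, the cohorts may turn out similar, and no direction can be given. The 1.3% to 7.3% rests wholly on the assumed distributions and correlations; it exceeds 3.2% only at r = 0.5 with an underlying mean of 500 or 600. Severity is minor to moderate.

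**What to change.** 1. Reconcile the CD4 statements in 8.1.1 and Appendix 11 with 2.1.1 and 2.1.2, without changing any entry threshold. Reconcile the secondary status of the HAART question (1.1, 5.2) with its place among the primary comparisons in 6.1.
2. Keep the planned 6.1 and 6.2 tests and their alpha levels.
3. Add to section 6, as the analysis of HAART use promised in 5.2 and with no alpha attached, three supportive estimates for Cohort 1 vs 2 on log10 titer: adjusted for age (sex optional); the same model with baseline CD4 added; and the comparison restricted to Cohort 1 patients with CD4 of at least 500. State that CD4 in Cohort 1 partly reflects HAART, and that the unrestricted CD4 model extrapolates at 350 to 499. A shared RNA ceiling does not make RNA distributions alike, so these analyses address CD4 and age only. The version is dated January 2019 and does not say whether titers have been analysed; if they have, label these analyses post hoc.
4. In 8.1.1, replace the claim about the impact of HAART with the difference between the HAART and no-HAART cohorts, and state that HAART status cannot be separated from route and duration of infection.

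The cost is a few sentences and a little analysis on age and CD4 data already collected. The supportive intervals may be wider than the unadjusted one. The stated power of the primary tests does not change.
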